8.3 Definitions of analysis sets

All efficacy analyses will be performed using an Intent-to-Treat (ITT) approach based on the full analysis set. For consistency, demographic, baseline characteristics and safety objectives will be presented using the full analysis set.

8.3.1 All subjects analysis set

This analysis set will comprise all subjects screened for the study and will be used for reporting of disposition and screening failures.

8.3.2 Full analysis set

The full analysis analysis set consists of all randomized subjects who received at least one dose of investigational product irrespective of their protocol adherence and continued participation in the study. Subjects will be analyzed according to the randomized treatment

assignment, irrespective of whether or not they have prematurely discontinued, according to the ITT principle. Subjects who withdraw consent, and assent when applicable to participate in the study will be included up to the date of their study termination. Subjects with data available for baseline and at least one post baseline assessment will be included in the corresponding analysis.

8.3.3 Safety analysis set

The safety analysis set will be the same as the full analysis set. Any major deviations from the randomized treatment assignment will be listed and considered when interpreting the safety data. All safety summaries will be based on this analysis set.

8.4 Outcome measures for analyses

8.4.1 Calculation or derivation of efficacy variables

This study has two main analysis parts for efficacy evaluations as described below:

1. Visit 4 up to Visit 10 to evaluate the effect on baseline inflammation
2. Screening Allergen Challenge, post-dose Allergen Challenge 1 and Allergen Challenge 2 to evaluate response to allergen challenge

The study also has two primary endpoints:

1. Allergen induced change in percentage of eosinophils in induced sputum at 7-hr post allergen challenge during Allergen Challenge 1,
2. Maximum percent decrease in FEV₁ in late asthmatic response (LAR)_{3-7 hr} during Allergen Challenge 1

8.4.1.1 Allergen induced change in percentage of eosinophils in induced sputum post allergen challenge during allergen challenge 1

There are 2 triads where percentages of eosinophils post allergen challenge are collected in the study – at Screening and at Allergen Challenge 1. At each triad, a pre-challenge, 7-hr and 24-hr post challenge samples will be taken (refer to table below for visit associated with measurements). The 7-hr post allergen challenge measure during allergen challenge 1 will be considered as primary.

Triad	Pre-challenge	7-hr post challenge	24-hr post challenge
Screening (pre-dose)	Visit 1	Visit 2	Visit 3
Allergen Challenge 1 (post-dose)	Visit 10	Visit 11	Visit 12

The allergen induced change at 7-hr and 24-hr post challenge will be derived by percentages of eosinophils post-challenge minus the percentages of eosinophils pre-challenge within each triad:

$$\text{Allergen Induced Change}_{\text{screening}} = \text{post-challenge}_{\text{screening}} - \text{pre-challenge}_{\text{screening}}$$

$$\text{Allergen Induced Change}_{\text{Allergen Challenge 1}} = \text{post-challenge}_{\text{Allergen Challenge 1}} - \text{pre-challenge}_{\text{Allergen Challenge 1}}$$

8.4.1.2 Maximum percent decrease in FEV₁ in late asthmatic response (LAR)_{3-7 hr} during allergen challenge

FEV₁ measurements will be taken for up to 7 hrs post-allergen challenge at the following 3 visits: Screening, Visit 11 (Allergen Challenge 1), and Visit 14 (Allergen Challenge 2).

Triad	Pre-challenge	Post-challenge LAR _{3-7 hr}
Screening (pre-dose)	Visit 2 pre-challenge	Visit 2 post challenge
Allergen Challenge 1 (post-dose)	Visit 11 pre-challenge	Visit 11 post-challenge
Allergen Challenge 2 (post-dose)	Visit 14 pre-challenge	Visit 14 post-challenge

Maximum percent decrease in FEV₁ in LAR_{3-7 hr} in each triad will be defined as 100* (Minimum value of FEV₁ between 3 – 7 hours post allergen challenge – pre-challenge value)/(pre-challenge value). The FEV₁ in LAR_{3-7 hr} on Visit 11 is considered as the primary endpoint.

8.4.1.3 AUC of time adjusted percent decrease in FEV₁ curve in late asthmatic response (LAR)_{3-7 hr} during allergen challenge

The total AUC for percent decrease FEV₁ in LAR_{3-7 hr} will be estimated using the linear trapezoidal rule (LxHour) using all available FEV₁ data between and inclusive of the 3 to 7 hours. The time adjusted total AUC FEV₁ in LAR_{3-7 hr} is calculated as total AUC/ (the length of time (hr) the total AUC is calculated).

8.4.1.4 Percentage of eosinophils in induced sputum for the effect on baseline inflammation

Eosinophils in induced sputum are collected on Visit 4 (pre-dose, will be defined as baseline for the summary of effect on baseline inflammation), and on Visit 7 and Visit 10. The change from baseline (Visit 4) of percent eosinophils to each post-baseline visit will be used in the analyses.

8.4.1.5 Basophil count in induced sputum for both allergen challenge and baseline inflammation

Similar to change from baseline of percent eosinophils in induced sputum, there are 2 types of measurements for basophil count in induced sputum: allergen induced change at 7-hr and 24-hr post allergen challenge to evaluate allergen response at Screening and Allergen Challenge 1, and measurements for effect on baseline inflammation at Visit 4, Visit 7 and Visit 10. Basophil count in sputum will be obtained by two types of readings: flow cytometry and cytopins with toluidine blue staining, refer to tables below for the scheduling of each type of reading.

Allergen Challenge related:

	Pre-challenge	7-hr post	24-hr post
Screening	cytopins with toluidine blue staining	cytopins with toluidine blue staining	cytopins with toluidine blue staining
Allergen Challenge 1	flow cytometry; cytopins with toluidine blue staining	cytopins with toluidine blue staining	flow cytometry; cytopins with toluidine blue staining

Baseline Inflammation related:

Visit 4 (baseline)	Visit 7	Visit 10
flow cytometry ; cytopins with toluidine blue staining	cytopins with toluidine blue staining	flow cytometry ; cytopins with toluidine blue staining

8.4.1.6 Maximum percent decrease in FEV₁ in early asthmatic response 0-2 hr (EAR_{0-2hr})

Maximum percent decrease in FEV₁ in EAR_{0-2 hr} at each visit will be defined as 100* (Minimum value of FEV₁ between 0 – 2 hours post allergen challenge – pre-challenge value)/(pre-challenge value).

8.4.1.7 AUC of time adjusted percent decrease in FEV₁ curve in early asthmatic response (EAR_{0-2 hr})

The total AUC for FEV₁ in EAR_{0-2 hr} will be estimated using the linear trapezoidal rule (LxHour) using all available FEV₁ data between and inclusive of the 0 to 2 hours. The time

adjusted total AUC FEV₁ in EAR_{0-2 hr} is calculated as total AUC/ (the length of time (hours) the total AUC is calculated).

8.4.1.8 Number of eosinophils and basophils in lung tissue biopsies for both allergen challenge and baseline inflammation

Biopsy samples are collected at Visit 5 (baseline), Visit 8 (pre allergen challenge), and Visit 15 (24-hr post challenge). Effect on baseline inflammation will be evaluated by change from baseline (Visit 5) to Visit 8. Effect on allergen response will be evaluated by change from pre-challenge (Visit 8) to post-challenge (Visit 15).

8.4.1.9 Eosinophil, eosinophil progenitor cells and basophils in bone marrow aspirates for both allergen challenge and baseline inflammation

Eosinophils, Eosinophil progenitor cells and basophils in bone marrow aspirates are collected in the bone marrow aspirate sub-group of subjects on Visit 4 (baseline), Visit 10 (pre-challenge) and Visit 12 (post-challenge).

Effect on baseline inflammation will be evaluated by change from Visit 4 to Visit 10. Effect on allergen response will be evaluated by change from pre-challenge (Visit 10) to post-challenge (Visit 12).

8.4.1.10 Eosinophils and basophils counts in the blood

Similar to percentage of eosinophils in induced sputum, there are 2 types of measurements for eosinophils: 1) allergen induced change to evaluate allergen response, and 2) measurements for effect on baseline inflammation at Visit 4, 7, 9 and 10. For basophil counts in blood only allergen challenge 1 is assessed for allergen induced change and Visit 4 and Visit 10 for baseline inflammation. For allergen induced change, see table below for corresponding visit:

For Eosinophils:

Triad	Pre-challenge	Post-challenge
Allergen Challenge 1 (post-dose)	Visit 10	Visit 11 and Visit 12
Allergen Challenge 2 (post-dose)	Visit 13	Visit 14 and Visit 15

For Basophils:

Triad	Pre-challenge	Post-challenge
Allergen Challenge 1 (post-dose)	Visit 10	Visit 12

8.4.1.11 Methacholine PC20 (concentration of inhaled methacholine that produces a 20% fall in FEV₁)

Similar to percentage of eosinophils in induced sputum, there are 2 types of measurements for Methacholine PC20: 1) allergen induced change to evaluate allergen response, and 2) measurements for effect on baseline inflammation at Visit 4, 7 and 10. For allergen induced change, see table below for corresponding visit:

Triad	Pre-challenge	Post-challenge
Screening (pre-dose)	Visit 1	Visit 3
Allergen Challenge 1 (post-dose)	Visit 10	Visit 12

8.4.1.12 Soluble inflammatory markers associated with pathology of asthma or the pharmacology of Benralizumab

Details of the analyses will be specified in a separate analyses plan.

8.4.2 Calculation or derivation of safety variables

8.4.2.1 Safety variables

The following safety data will be collected: vital signs, physical examination and ECG, haematology, clinical chemistry, urinalysis, reported AEs and SAEs.

8.5 Methods for statistical analyses

Demographics and subject characteristics will be summarized by treatment group using frequency and percentages (for categorical variables) and descriptive statistics of mean, standard deviation, minimum, median and maximum (for continuous variables) using the full analysis set.

The prior medications, categorized according to the WHO Drug Reference List dictionary which employs the Anatomical Therapeutic Chemical (ATC) classification system, will be summarized by treatment group as frequency and percentage of subjects reporting usage.

The concomitant medication will be categorized according to the WHO Drug Reference List dictionary which employs the Anatomical Therapeutic Chemical (ATC) classification system. The frequency and percentage of subjects taking concomitant medications and non-drug therapies during the treatment period will be summarized by drug class and drug name using ATC code.

The analysis of the primary, secondary and exploratory endpoints will include all data captured during the study, unless the subject withdraws consent, and assent when applicable to

study participation, regardless of whether study treatment was prematurely discontinued, or delayed, and/or irrespective of protocol adherence.

Descriptive statistics will also be provided for safety and efficacy data. Unless otherwise stated, the data analysis include subjects in the full analysis set. Descriptive statistics on continuous variables will be summarized by treatment group using mean, standard deviation, minimum, median and maximum, while categorical data were summarized using frequency counts and percentages. When data are summarized by time, the values recorded against the scheduled time points listed in the protocol were used. When assessing minimum/maximum increases or decreases during the study, all assessments, including unscheduled assessments will be used. For analysis assessing change from baseline, only subjects with both baseline and at least 1 evaluable post-baseline measure will be included. Nominal visit will be used for all summary and analysis, no analysis window will be applied.

Testing strategy to account for multiplicity considerations

There are two primary endpoints, the allergen induced change in percentage of eosinophils in sputum 7-hr post allergen challenge and maximum percent decrease in FEV₁ in the late asthmatic response on Visit 11. These endpoints will be tested using the following hierarchical fixed-sequence approach in order to control the overall type I error rate at the 0.05 level:

Step 1 first perform the test on allergen induced change in percentage of eosinophils in sputum 7-hr post allergen challenge. If the p-value is ≤ 0.05 , then proceed with Step 2. Otherwise, neither of the two hypothesis will be rejected.

Step 2 perform the test on maximum percent decrease in FEV₁ in the late asthmatic response on Visit 11, at alpha level of 0.05.

8.5.1 Analysis of the primary variable (s)

8.5.1.1 Allergen induced change in percentage of eosinophils in induced sputum 7-hr post allergen challenge during Allergen Challenge 1

The null hypothesis is that the allergen induced change in percentage of eosinophils in induced sputum 7-hr post allergen challenge during Allergen Challenge 1 in the Benralizumab group is equal to the allergen induced change in percentage of eosinophils in induced sputum 7-hr post allergen challenge during Allergen Challenge 1 in the Placebo group. The alternative hypothesis is that the allergen induced change in percentage of eosinophils in induced sputum 7-hr post allergen challenge during Allergen Challenge 1 in the Benralizumab group is not equal to that in Placebo group, ie,:

*H*₀: Allergen Induced Change_{7-hr post challenge at Allergen Challenge 1 (Benralizumab)} = Allergen Induced Change_{7-hr post challenge at Allergen Challenge 1 (Placebo)}

*H*_a: Allergen Induced Change_{7-hr post challenge at Allergen Challenge 1 (Benralizumab)} \neq Allergen Induced Change_{7-hr post challenge at Allergen Challenge 1 (Placebo)}

The primary analysis method for the allergen induced change on Visit 11 (7-hr post challenge) and 12 (24-hr post challenge) will be compared between Benralizumab and Placebo using a repeated measures analysis. The dependent variable will be the allergen induced change in percentage of eosinophils in induced sputum at 7-hr and 24-hr post allergen. Treatment group will be fitted as an explanatory variable pre-dose allergen induced change at Screening will be fitted as a covariate. Visit will be fitted as a categorical variable, and the variance-covariance matrix will be assumed to be unstructured. If the procedure does not converge the compound symmetric variance-covariance matrix will be used instead. The least squares mean for the difference in treatment groups using the interaction between visit and treatment group its 95% CI, and the 2-sided p-values will be reported for each visit.

8.5.1.2 Maximum percent decrease in FEV₁ in late asthmatic response (LAR_{3-7 hr}) on Visit 11 during Allergen Challenge 1

The null hypothesis is that the maximum percent decrease in FEV₁ in late asthmatic response (LAR_{3-7 hr}) on Visit 11 in Benralizumab group is equal to the maximum percent decrease in FEV₁ in late asthmatic response (LAR_{3-7 hr}) on Visit 11 in Placebo group. The alternative hypothesis is that the maximum percent decrease in FEV₁ in late asthmatic response (LAR_{3-7 hr}) on Visit 11 in Benralizumab group is not equal to that in Placebo group, ie,:

H₀: Maximum percent decrease in FEV₁ in LAR_{3-7 hr} visit 11 (Benralizumab) = Maximum percent decrease in FEV₁ in LAR_{3-7 hr} Visit 11 (Placebo)

H_a: Maximum percent decrease in FEV₁ in LAR_{3-7 hr} visit 11 (Benralizumab) ≠ Maximum percent decrease in FEV₁ in LAR_{3-7 hr} Visit 11 (Placebo)

Maximum percent decrease in FEV₁ at LAR_{3-7 hr} on Visit 11 will be compared between Benralizumab and Placebo using an ANCOVA. The dependent variable will be maximum percent decrease in FEV₁ at LAR_{3-7 hr}. Treatment group will be fitted as an explanatory variable and the corresponding pre-dose FEV₁ value at Screening will be fitted as a covariate. The least squares mean for the difference in treatment groups and its 95% CI, and the 2-sided p-values will be provided.

As a supportive analysis to the primary analyses the time adjusted AUC of FEV₁ at LAR_{3-7 hr} will be analyzed and summarized descriptively as for maximum percent decrease in FEV₁.

The above analyses will be repeated at allergen challenge 2 triad.

FEV₁ at both pre- and post-challenge timepoints and minimum FEV₁ post-challenge for LAR_{3-7 hr} will also be summarized descriptively by visit (Visit 2, 11 and 14).

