Approximately 38 subjects in total and 19 subjects in each treatment group are needed for this study based on the choice of two primary endpoints; the change in percentage of eosinophils in induced sputum at 7-hr post allergen challenge and the maximum percent decrease in FEV₁ in late asthmatic response (LAR_{3-7 hr}) both measured after the first allergen challenge. These endpoints will be tested using a hierarchical fixed-sequence approach, the first assessment being the effect on percentage of eosinophils in sputum.

Subjects will be randomized in a 1:1 ratio to benralizumab or placebo. In order to have balanced number of subjects for the outcomes from induced sputum, blood, bone marrow and bronchoscopy measures, randomization will be stratified by the following types of

measurements: 1) bone marrow plus bronchoscopy measurements, 2) bronchoscopy measures only, and 3) neither bone marrow nor bronchoscopy measurements.

The primary analysis method for the allergen induced change in percentage of eosinophils in induced sputum at 7-hr and 24-hr post challenge 1 will be compared between Benralizumab and Placebo using a repeated measures analysis. Treatment group will be fitted as an explanatory variable, pre-dose allergen induced change at Screening will be fitted as a covariate and visit will be fitted as a categorical variable.

The maximum percent decrease in FEV_1 at $LAR_{3-7\text{ hr}}$ will be compared between Benralizumab and Placebo using an ANCOVA. Treatment group will be fitted as an explanatory variable and the corresponding pre-dose FEV_1 value at Screening will be fitted as a covariate.

Efficacy analysis will be performed using the full analysis set, which consists of all randomized subjects who received at least one dose of investigational product.

All safety variables will be summarised descriptively. Safety analysis will be performed in safety analysis set which is the same as full analysis set.

TABLE OF CONTENTS	PAGE
TITLE PAGE.....	1
VERSION HISTORY	2
PROTOCOL SYNOPSIS	8
TABLE OF CONTENTS	13
1. INTRODUCTION	20
1.1 Background and rationale for conducting this study	20
1.2 Rationale for study design, doses and control groups.....	21
1.3 Benefit/risk and ethical assessment	22
1.4 Study Design.....	24
2. STUDY OBJECTIVES.....	27
2.1 Primary objective	27
2.2 Secondary objectives.....	27
2.3 Safety objectives	28
2.4 Exploratory objectives	29

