3.1 Inclusion criteria

For inclusion in the study subjects should fulfil the following criteria:

1. Written informed consent for study participants must be obtained prior to any study related procedures being performed and according to local guidelines.
2. Female or male aged 18 to 65 years, inclusively, at the time of enrolment.

3. General good health as declared by the investigator
4. Mild, stable, allergic asthma and asthma therapy limited to inhaled, short-acting β_2 agonists (should not be used in more than 2 occasions in a week). If the subject uses the short-acting β_2 agonist for prophylactic treatment this should not be included in the number of times that it is used in a 1 week-period
5. Ability to produce a sputum sample and viable cytospin for assessment of the cell differential count at screening pre, 7 and 24 hours post- challenge
6. History of episodic wheeze and shortness of breath; Pre-bronchodilator FEV₁ at screening of at least 70% of the predicted value

7. No current exposure to allergens to which a subject experiences asthmatic responses (with the exception of the house dust mite).
8. Positive methacholine challenge ($PC_{20} \leq 16$ mg/mL) at screening
9. Positive skin-prick test to at least one common aeroallergen (including but not limited to cat, dust mite, grass/tree pollen) at screening
10. Positive early and late airway responses during the screening allergen challenge. The early response will be a fall in FEV1 of $\geq 20\%$ during the two hours after allergen challenge. The late response will be defined as a fall in FEV1 of $\geq 15\%$ during the 3-7 hours after allergen inhalation.
11. Demonstrate an increase in sputum eosinophils at 7 hrs post allergen challenge relative to the pre allergen challenge sputum sample at screening.
12. Women of childbearing potential (WOCBP) must use an effective form of birth control (confirmed by the Investigator). Effective forms of birth control include: true sexual abstinence, a vasectomized sexual partner, Implanon, female sterilization by tubal occlusion, any effective IUD intrauterine device/IUS levonorgestrel Intrauterine system, Depo-Provera™ injections, oral contraceptive, and Evra Patch™ or Nuvaring™. WOCBP must agree to use effective method of birth control, as defined above, from enrolment, throughout the study duration and within 16 weeks after last dose of IP, and have negative serum pregnancy test result on Visit 1.

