Maximum decreases in FEV₁ will be chosen to quantify the early and late response magnitudes.

The FEV₁ will then be measured at regular intervals until 7 hours post allergen inhalation: 10, 20, 30, 45, 60, 90, 120, 180, 240, 300, 360 and 420 minutes post allergen inhalation.

The early bronchoconstrictor response (i.e., EAR) is taken to be the largest percentage fall in FEV₁ within 2 hours post allergen inhalation, and the late response (i.e., LAR) is taken to be the largest percentage fall in FEV₁ between 3 hours and 7 hours post allergen inhalation. The area under the curve (AUC) is determined during the early (0-2 h) and late (3-7 h) responses. Only subjects who achieve a fall in FEV₁ of ≥20% during the period of early response and a fall in FEV₁ of ≥15% during the period of late response at screening V2 will be randomised.

Post treatment Allergen Challenge Triads

The same doses of allergen as used at screening are administered during each subsequent challenge unless it is unsafe to do so. If this happens the procedure will proceed with the highest allergen dose that can be administered as outlined in [REDACTED] SOPs.

Note: If the subject has to use inhaled or oral corticosteroids, the remaining secondary and exploratory outcomes of the allergen challenge triad should be aborted. Subjects will report for safety assessments, including spirometry.

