The change from pre-allergen challenge eosinophils counts in blood after allergen challenge will be analysed using a repeated measures approach separately for the Allergen Challenge 1 and 2 triads. The dependent variable will be the allergen induced change in absolute eosinophil counts at 7-hr and 24-hr post challenge. Treatment group will be fitted as an explanatory variable and baseline (Visit 4) will be fitted as a covariate. Visit (7-hr, 24-hr) will be fitted as a categorical variable, and the variance-covariance matrix will be assumed to be unstructured. If the procedure does not converge the compound symmetric variance-covariance matrix will be used instead. The least squares mean for the difference in treatment groups using the interaction between visit and treatment group its 95% CI, and the 2-sided p-values will be reported for each visit.

The change from pre-allergen challenge in the number of eosinophils and basophils in lung tissue biopsies will be analysed using an ANCOVA. The dependent variable will be the change in the number of eosinophils and absolute basophils in lung tissue biopsies from Visit 8 to Visit 15. Treatment group will be fitted as an explanatory variable and baseline (Visit 5) will be fitted as a covariate.

Allergen induced change in methacholine PC20 at Allergen Challenge 1 will be analysed using ANCOVA with treatment as explanatory variable and allergen induced change at Screening fitted as a covariate.

Endpoints for secondary objectives to evaluate the effect on *baseline inflammation* in this study are:

- Percentage of eosinophils in induced sputum for the effect on baseline inflammation
- Eosinophils and basophils counts in blood
- Number of eosinophils and basophils in lung tissue biopsies
- Basophil count in induced sputum from cytopins with toluidine blue staining

The primary timepoint for this evaluations will be Visit 10 (except Visit 8 for bronchoscopy measures).

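### As worded, the ANCOVA for the late asthmatic response adjusts for a screening FEV₁ value; naming the screening late-phase percent fall would settle the wording and probably gain precision at no cost

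*Protocol*

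**What the plan says.** Protocol section 8.5.1.2 compares the arms on the maximum percent decrease in FEV₁ at 3-7 h on Visit 11 by ANCOVA. Treatment is the explanatory variable and "the corresponding pre-dose FEV₁ value at Screening will be fitted as a covariate". The statistical methods part of the synopsis says the same. No other covariate is named.

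The same model is reused. Section 8.5.1.2 applies it to the time-adjusted AUC of the late response and repeats the analyses at Allergen Challenge 2. Section 8.5.2 analyses the early response in the same way.

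Two other endpoints with a screening counterpart are treated differently:
- Sputum eosinophils (8.5.1.1): "pre-dose allergen induced change at Screening will be fitted as a covariate".
- Allergen-induced change in methacholine PC20 (8.5.2): treatment, with "allergen induced change at Screening fitted as a covariate".

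The screening late response exists for every eligible subject. Section 3.1 requires "Positive early and late airway responses during the screening allergen challenge", and section 5.1.1 limits randomisation to those who also show "a fall in FEV₁ of ≥15% during the period of late response at screening V2 will be randomised". Section 8.4.1.2 defines the maximum percent decrease by one formula for each triad, Screening included.

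**The concern.** The endpoint is a percent fall, already divided by the same day's pre-challenge FEV₁, so most of the information about lung size has been removed from it. A screening FEV₁ level would be expected to say little about how far FEV₁ falls in percent after allergen. The natural baseline is the same percent fall at the screening challenge, measured in the same subject with the same allergen and, unless unsafe, the same doses (section 5.1.1).

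What is at stake is precision, plus correction for chance imbalance in late responsiveness between two arms of 19. By the planning figures in section 8.2, the late response is also the tighter of the two primary tests: 11/12 = 0.92 SD, against 0.8 × 20.8/17.3 = 0.96 SD for sputum eosinophils. It comes second in the fixed sequence. A further cost is that the covariate of a primary test can be read in more than one way.

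**Working it through.** **Inputs.** Section 8.2 gives a difference of 11 percentage points, SD 12, two-sided 5% alpha, 80% power and 19 per group. The correlation r between the covariate and the Visit 11 fall, within arm, is not in the documents. It is an assumption, shown as a range.

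**Step 1: the plan's own figure.** Normal approximation: n per group = 2 × (1.960 + 0.842)² × 12²/11² = 18.7, rounded up to 19. This matches the protocol and contains no covariate term. With the t distribution, power at 19 per group is 78.5% and 20 per group would be needed for 80%. The stated size therefore does not depend on which covariate is fitted.

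**Step 2: effect of a covariate.** Residual SD = 12 × √(1 − r²). Standard error of the difference = residual SD × √(2/19). The 95% CI half-width is t(0.975, 35 df) × standard error, with t = 2.03. Power comes from the noncentral t with 2 × 19 − 3 = 35 df.

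| r | Residual SD | CI half-width | Power at 19 per arm | n per arm for 80% |
|---|---|---|---|---|
| 0 | 12.0 | 7.9 | 78.4% | 20 |
| 0.1 | 11.9 | 7.9 | 78.8% | 20 |
| 0.3 | 11.4 | 7.5 | 82.1% | 19 |
| 0.4 | 11.0 | 7.2 | 85.0% | 17 |
| 0.5 | 10.4 | 6.8 | 88.7% | 16 |

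The rows for 0 and 0.1 stand for an FEV₁ level, if it is as weakly related to the percent fall as expected. The rows for 0.3 to 0.5 stand for the screening percent fall. Across that range the residual variance drops by r², that is by 9% to 25%.

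**Step 3: the entry rule.** Admitting only subjects with a late fall of at least 15% narrows the range of the covariate and weakens r. A simulation assumed normally distributed screening falls with mean 15-25 and SD 8-12. After truncation at 15, a correlation of 0.5 became 0.33-0.44. To keep 0.5 or more after selection, the untruncated correlation would have to be near 0.7 (which became 0.51-0.63). The lower and middle rows are therefore the more realistic.

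**Step 4: what the words can mean.** The tables in section 8.4.1 label the whole Screening triad pre-dose, so the phrase has three possible readings:
- the Visit 2 pre-challenge FEV₁;
- the Visit 2 minimum FEV₁ at 3-7 h;
- loosely, the screening late-phase percent fall.

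These are three different models and need not give the same estimate or p-value.

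**The case against.** The strongest reply is that the screening percent fall was intended all along. In this protocol 'pre-dose' means before study drug, and the FEV₁ level before allergen has its own term, 'pre-challenge'. Section 8.4.1.2 itself loosely calls the percent-fall endpoint FEV₁ in the late response. 'Corresponding' follows directly on the dependent variable and makes most sense if it points to the same quantity at Screening. This stands as a plausible reading. A reader might infer that the plan definitely discards the screening response, and the documents do not support that. Even so, the words as written name an FEV₁ value, in both places, and a programmer following them literally would fit a less precise model.

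A second reply is that covariate derivations belong in the SAP, which is not shown here. That is fair for missing detail. Here, though, the protocol names the covariate, and the wording it fixes is the problem.

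A third reply is that nothing is invalid even on the literal reading. This stands in full. In a randomised comparison a weak baseline covariate causes no bias and no type I error inflation, and the stated 19 per group was reached without one.

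The last reply is that the size of the gain is not grounded in the documents. This largely stands. No correlation is given, the entry rule restricts the range, and SD 12 comes from a cited study not available here. If that SD is already a covariate-adjusted residual, the gains in the table are overstated.

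**Conclusion.** The covariate is worded as an FEV₁ value for a percent-fall endpoint. That is out of line with the plan's own handling of sputum eosinophils and PC20 change, and it can be read in more than one way. Naming the screening late-phase percent fall is a precision gain from data already collected.

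Its likely size, for an assumed r of 0.3 to 0.5, is power of about 82-89% in place of about 78%, and a CI half-width of about 7.5-6.8 points in place of 7.9. The upper end is less likely because of the 15% entry rule. This rests on SD 12 being an unadjusted SD and on the FEV₁ level being nearly uncorrelated with the percent fall.

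A reader might infer that the primary test is biased or that the sample size is wrong. Neither follows: the comparison remains valid under either covariate, and 19 per group reproduces with none. This is an efficiency improvement and a clarification, and does not make the planned analysis invalid.

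**What to change.** Before unblinding, change the covariate in the synopsis and in section 8.5.1.2 together to the maximum percent decrease in FEV₁ (3-7 h) at the screening challenge, Visit 2. For the analyses that borrow this model, name the matching screening measure: the screening AUC for the late-response AUC, the screening maximum fall at 0-2 h for the early-response maximum fall, and the screening early-response AUC for its AUC. Carry the same definitions into the SAP, which section 8.1 says is to be completed before unblinding.

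The cost is one sentence in two places and a line for the dependent analyses. No new data, visits or subjects are needed.
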